## Part 2: Expansion Phase

For the arms which show promise for efficacy in part 1 (based on pre-defined criteria), these arms may be expanded.

After completion of the expansion phase and within each arm separately, the following statistical hypothesis will be tested based on objective response rate (ORR):

- The null hypothesis is that the response rate is not clinically meaningful ( $\leq 10\%$ ).
- The alternative hypothesis is that the response rate is clinically meaningful ( $>10\%$ ).  
The target response rate that warrants further development is  $\geq 25\%$

The null hypothesis will be formally rejected if the lower bound of exact 95% CI for ORR is above 10%. The primary analysis of ORR at the end of part 2 will be based on a combined pool of part 1 and part 2 data for given arm.

For example, assuming 24 subjects enrolled in an arm of interest in part 1 (see [Section 10.8.1](#) for sample size estimates when true ORR = 0.25 in the selection phase), assuming this arm met criteria for expansion and finally assuming 50 subjects are enrolled in the expansion phase, then combined among 74 subjects enrolled in this arm in total and followed sufficiently, 14 or more responses need to be observed to reject the null hypothesis. With those 14 responders among 74 subjects, the point estimate for ORR will be 18.9% with an exact 95% confidence interval of (10.8%, 29.7%). Since the lower bound of the exact 95% CI will be  $> 10\%$ , this leads to rejection of null hypothesis. The exact 95% CIs for potential observed ORR in 74 subjects are shown in [Table 10-2](#):

**Table 10-2 Exact binomial 95% confidence intervals around potential observed ORR for N=74**

Number of responders	Observed ORR (%)	95% exact CI (%)
10	13.5	6.7, 23.5
11	14.9	7.7, 25.0
12	16.2	8.7, 26.6
13	17.6	9.7, 28.2
14	18.9	10.8, 29.7
15	20.3	11.8, 31.2
16	21.6	12.9, 32.7
17	23.0	14.0, 34.2
18	24.3	15.1, 35.7
19	25.7	16.2, 37.2
20	27.0	17.4, 38.6
21	28.4	18.5, 40.1
22	29.7	19.7, 41.5
23	31.1	20.8, 42.9
24	32.4	22.0, 44.3

Fifty subjects enrolled in the expansion phase considered in the example above also correspond to the number of subjects needed to ensure that the hypothesis to be tested after completion of part 2 has sufficient predictive power conditioned on the ORR observed in the selection phase (part 1) (see [Section 10.8.1](#)).

### Alpha control considerations:

For each arm (treatment combination cohort) included in the study the potential for alpha inflation arises from the adaptive nature of the design and, in particular, from the presence of a selection process based on probabilistic decision rules described in [Section 10.4.2.1](#).

To assess whether alpha is controlled for each combination treatment arm separately, simulations were conducted. Below in [Table 10-3](#), simulation results for scenarios that include one or more arms with the true ORR of 0.10 corresponding to the null hypothesis threshold (see also Scenarios 1 and 2 in [Section 10.8.1](#)), are presented. Scenario 2 is investigated to assess a potential impact of shrinkage estimator on type I error inflation. In simulations, the focus was on assessing type I error for each of the ‘null hypothesis’ arm separately defined as the proportion of significant results after completion of part 2 for given arm (successful arm). The technical details for the simulations will be summarized in the SAP Appendix:

As shown in [Table 10-3](#), for each of the ‘null hypothesis’ arms with the true ORR=0.10 the probability is less than 0.025 (ranging between 0.0097 and 0.0149) and therefore alpha is well-controlled. Even though there is no explicit alpha control measure used, alpha within each arm is still well-controlled due to the use of the futility criterion in the selection phase, as well as the adaptive nature of the sample size of part 2, based on the shrinkage estimator. Further simulation results for alpha for other scenarios and under a wide variety of samples sizes for the expansion arm will be presented in the SAP Technical Appendix.

**Table 10-3 Type I error assessment: Probability of a successful result for scenario where the true ORR equals 0.10 for each arm and sample size of the expansion arm is 50 subjects**

[figure not shown]
Scenario	Arm	True ORR	Probability of significant result
1	1	0.10	0.0102
1	2	0.10	0.0104
1	3	0.10	0.0136
1	4	0.10	0.0097
2	1	0.10	0.0101
2	2	0.10	0.0111
2	3	0.10	0.0149
2	4	0.25	NA*
3	1	0.10	0.0102
3	2	0.25	NA*
3	3	0.25	NA*
3	4	0.25	NA*

\*NA=not applicable in the context of type I error assessment; applicable only to the arms with true ORR=0.10 corresponding to the null hypothesis

Note: No type I error rate control measures will be used to address the testing across several treatment arms considering that each combination treatment included in the design represents a stand-alone scientific question of interest leading to a stand-alone null hypothesis independent of other arms and thus allowing for one specific claim of statistical significance for the given arm.

### 10.4.2.2 Non-randomized section of the study

#### Part 1: Selection Phase

No formal hypothesis testing will be conducted in part 1. The objective of this part of the study is to explore the anti-tumor activity of the combination of spartalizumab with LAG525 agent in subjects with LAG-3 positive melanoma as measured by ORR per RECIST v1.1, and to expand this new arm if it shows promising efficacy.

To determine whether the arm has the potential to demonstrate clinically meaningful response rate, a specific efficacy probabilistic threshold should be met during the selection phase to advance to the expansion phase. If not, the arm will be declared as futile and won't be expanded. These thresholds and probabilities are highlighted in [Table 10-4](#).

**Table 10-4 Probabilities thresholds used to declare efficacy or futility for arm 1A**

Decision rule	Action
$P(\text{ORR} \geq 20\%) \leq 70\%$	Drop arm for futility
$P(\text{ORR} \geq 20\%) > 70\%$	Efficacy signal - Consider advancing arm to expansion phase (part 2)

The efficacy probabilistic threshold and decision criterion was determined so that a sufficient signal of efficacy needs to be observed before advancing this arm to the expansion phase and to ensure that if the true underlying ORR is 30% (clinically meaningful ORR) then the probability of crossing the threshold is sufficiently large (refer to [Table 10-12](#)).

To calculate the posterior probabilities, a beta-binomial posterior distribution will be used as shown below:

$$p \sim \text{beta}(y + 1, n - y + 1)$$

Where  $y$  is the number of confirmed responses in arm 1A and  $n$  is the number of subjects treated. In calculation of the posterior distribution, uninformed prior Beta[1,1] will be taken into account. The posterior probability will be calculated based on the observed ORR using RECIST v1.1 criteria at interim analysis as described in [Section 10.7.2](#).

The final decision on whether the arm will be selected for advancement to the expansion phase will primarily be based on the observed ORR using decision rule described above but other efficacy (in particular duration of response), safety, and biomarker data will be considered as well. Novartis may decide to not expand the arm despite the efficacy probability threshold crossed.

With 20 treated patients, 5 or more responders need to be observed to meet the efficacy probabilistic threshold as illustrated in [Table 10-5](#).

**Table 10-5 Posterior probability ORR≥20% given observed ORR at time of 1st interim analysis of selection phase**

# of Responders out of 20	ORR observed (%)	PP(ORR≥20%   observed ORR) (%)
0	0	0.9
1	5	5.8
2	10	17.9
3	15	37.0
4	20	58.6
5	25	76.9
6	30	89.1
7	35	95.7
8	40	98.9

# of Responders out of 20	ORR observed (%)	PP(ORR≥20%   observed ORR) (%)
9	45	99.6
10	50	99.9

## Part 2: Expansion Phase

If the pre-defined efficacy probabilistic threshold is met after the selection part, the arm 1A might be expanded.

A second interim analysis will be conducted including 20 additional patients treated in the expansion phase as described in Section 4.2.2, i.e. based on the total of 40 patients. The objective of this second interim analysis is to support and inform decision-making on whether arm 1A will be : (1) further explored (2) stopped for futility . To determine whether arm 1A has the potential to demonstrate clinically meaningful ORR, an efficacy probabilistic threshold same as in part 1 will need to be crossed (see Table 10-4). If not, the arm 1A will be declared futile and further exploration/enrollment will be stopped in this combination. With 40 subjects at time of 2nd interim analysis treated in arm 1A (combining part 1 and part 2), 9 responders will have to be observed to cross the efficacy probabilistic threshold (see Table 10-6 below).

**Table 10-6** Posterior probability ORR≥20% given observed ORR at time of 2nd interim analysis in expansion phase

# of responders at 2 nd IA out of 40 pts	ORR observed (%)	PP(ORR≥20%   observed ORR) (%)
5	12.5	14.4
6	15.0	26.1
7	17.5	40.7
8	20.0	56.2
9	22.5	70.4
10	25.9	81.8
Of note, 5 responders have to be seen at the 1 st interim analysis to advance in the expansion and reach the point of 2 nd interim analysis		

If efficacy probabilistic threshold is met at the 2nd interim analysis enrollment may continue in expansion up to approximately 80 subjects (i.e. 100 subjects in total adding the subjects in part 1).

After completion of the expansion phase, the following statistical hypothesis will be tested based on objective response rate (ORR):

- The null hypothesis: ORR ≤ 15%.
- The alternative hypothesis: ORR >15%

The null hypothesis will be formally rejected if the lower bound of exact 95% CI for ORR is above 15%. The primary analysis of ORR at the end of part 2 will be based on a combined pool of part 1 and part 2 data.

For example, assuming the scenario when 20 subjects are treated in part 1, efficacy probabilistic thresholds at 1st and 2nd interim analysis are met and the total of 80 subjects is treated in the expansion phase then among 100 subjects treated in this arm in total and followed sufficiently, 23 or more responses need to be observed to reject the null hypothesis. With those 23 responders among 100 subjects, the point estimate for ORR will be 23% with

an exact 95% confidence interval of (15.2, 32.5). The exact 95% CIs for potential observed ORR in 100 subjects are shown in [Table 10-11](#) of [Section 10.8.2](#).

### **10.4.3 Handling of missing values/censoring/discontinuations**

For the computation of ORR, all confirmed responses (CR or PR) reported up to the analysis cut-off will be included. Subjects with no valid radiological assessment or unconfirmed responses will be considered as non-responders. Subjects who were non-responders before initiation of subsequent anti-cancer therapy will still be non-responders. In particular, subjects with CR or PR at the last radiological assessment prior to cut-off and no response at the previous assessment are by definition unconfirmed and will be considered as non-responders for the primary analysis.

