### **7.2.1.2 Post-baseline imaging assessments**

Imaging assessments as described in [Table 7-3](#) should be performed at the time points specified using the same imaging modality used at baseline, irrespective of study treatment interruption or actual dosing (see [Table 7-2](#)). Imaging assessments for response evaluation will be performed 12 weeks ( $\pm 7$  days) after the date of randomization (or after the date of first dose of study treatment in arm 1A), then every 8 weeks ( $\pm 7$  days) until 52 weeks after randomization/date of first dose of study treatment in arm 1A, and every 12 weeks ( $\pm 7$  days) thereafter until disease progression per RECIST 1.1 (as assessed by the investigator), death, lost to follow-up or withdrawal of consent. Imaging assessments should be scheduled using the randomization date (or after the date of first dose of study treatment in arm 1A) as the reference date (not the date of the previous tumor assessment), and should be respected regardless of whether treatment with study treatment is temporarily withheld or unscheduled assessments performed.

An additional tumor assessment must be performed to confirm response (complete response CR or partial response PR) as per RECIST v1.1, no less than 4 weeks after the criteria for response are first met.

For subjects who discontinue study treatment without disease progression per RECIST v1.1 (as assessed by the investigator), imaging assessments must be performed as part of efficacy follow up as described in [Table 7-2](#) and [Table 7-3](#) until disease progression per RECIST v1.1 (as assessed by the investigator), death, lost to follow-up or withdrawal of consent.

Every effort will be made to continue collection of tumor assessments even after the start of subsequent anti-cancer therapy for subjects that have not progressed.

For all subjects (including those who continue study treatment beyond disease progression per RECIST v1.1), at least two additional tumor assessments that are at least 4 weeks apart are recommended subsequent to disease progression per RECIST v1.1 [REDACTED] no less than 4 weeks after criteria for disease progression per RECIST v1.1 are first met. Tumor assessments after start of new anti-cancer therapy are recommended.

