### 10.4.1 Variable

Objective response rate (ORR) is defined as the proportion of subjects with best overall response (BOR) of either confirmed complete response (CR) or confirmed partial response (PR), as per local review and according to RECIST v1.1 (see Appendix 2 for details).

[REDACTED]

ORR will be calculated based on the FAS. ORR and its 95% confidence interval will be presented by treatment group.

As a supportive analysis, ORR as per blinded independent central review (BICR) will be presented by treatment group; along with 95% confidence intervals (see [Section 10.4.4](#)).

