- PR = at least two determinations of PR or better at least 4 weeks apart before progression (and not qualifying for a CR) where confirmation required or one determination of PR prior to progression where confirmation not required
- SD = at least one SD assessment (or better) > 11 weeks after randomization/start of treatment (and not qualifying for CR or PR).
- PD = progression ≤ 12 weeks after randomization/ start of treatment (and not qualifying for CR, PR or SD).
- UNK = all other cases (i.e. not qualifying for confirmed CR or PR and without SD after more than 11 weeks or early progression within the first 12 weeks)

The time durations specified in the SD/PD/UNK definitions above are based on the first 12-week tumor assessment frequency taking into account time windows for assessment. E.g. if the first assessment occurs at week 12 with a time window of +/- 7 days, a BOR of SD would require a SD or better response longer than 11 weeks after randomization/start of treatment.

Overall lesion responses of CR must stay the same until progression sets in, with the exception of a UNK status. A subject who had a CR cannot subsequently have a lower status other than a PD, e.g. PR or SD, as this would imply a progression based on one or more lesions reappearing, in which case the status would become a PD.

Once an overall lesion response of PR is observed (which may have to be a confirmed PR depending on the study) this assignment must stay the same or improve over time until progression sets in, with the exception of an UNK status. However, in studies where confirmation of response is required, if a subject has a single PR (≥30% reduction of tumor burden compared to baseline) at one assessment, followed by a <30% reduction from baseline at the next assessment (but not ≥20% increase from previous smallest sum), the objective status at that assessment should be SD. Once a confirmed PR was seen, the overall lesion response should be considered PR (or UNK) until progression is documented or the lesions totally disappear in which case a CR assignment is applicable. In studies where confirmation of response is not required after a single PR the overall lesion response should still be considered PR (or UNK) until progression is documented or the lesion totally disappears in which case a CR assignment is applicable.

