Example: In a case where confirmation of response is required the sum of lesion diameters is 200 mm at baseline and then 140 mm - 150 mm - 140 mm - 160 mm - 160 mm at the subsequent visits. Assuming that non-target lesions did not progress, the overall lesion response would be PR - SD - PR - PR - PR. The second assessment with 140 mm confirms the PR for this subject. All subsequent assessments are considered PR even if tumor measurements decrease only by 20% compared to baseline (200 mm to 160 mm) at the following assessments.

If the subject progressed but continues study treatment, further assessments are not considered for the determination of best overall response.

Note: these cases may be described as a separate finding in the CSR but not included in the overall response or disease control rates.

The best overall response for a subject is always calculated, based on the sequence of overall lesion responses. However, the overall lesion response at a given assessment may be provided from different sources:

- Investigator overall lesion response
- Central Blinded Review overall lesion response
- Novartis calculated overall lesion response (based on measurements from either Investigator or Central Review)

The primary analysis of the best overall response will be based on the sequence of investigator overall lesion responses.

Based on the subjects' best overall response during the study, the following rates are then calculated:

**Overall response rate (ORR)** is the proportion of subjects with a best overall response of CR or PR. This is also referred to as 'Objective response rate' in some protocols or publications.

**Disease control rate (DCR)** is the proportion of subjects with a best overall response of CR or PR or SD. The objective of this endpoint is to summarize subjects with signs of "activity" defined as either shrinkage of tumor (regardless of duration) or slowing down of tumor growth.

**Clinical benefit rate (CBR)** is the proportion of subjects with a best overall response of CR or PR, or an overall lesion response of SD or Non-CR/Non-PD which lasts for a minimum time duration (with a default of at least 24 weeks in breast cancer studies). This endpoint measures signs of activity taking into account duration of disease stabilization.

Another approach is to summarize the progression rate at a certain time point after baseline. In this case, the following definition is used:

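### Section 10.4.3 scores as non-responders some subjects whom Appendix 2 counts as confirmed: PR-SD-PR or PR-UNK-PR ending at the last scan before cut-off

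*Protocol*

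**What the plan says.** Section 10.4.1 defines ORR as the share of subjects whose best overall response, by local review, is a confirmed CR or PR, and refers to Appendix 2 for the details.

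Appendix 2, Section 14.2.3.1, gives the rule: "PR = at least two determinations of PR or better at least 4 weeks apart before progression". It does not ask for consecutive scans. If a first PR is followed by a scan with less than 30% shrinkage, "the objective status at that assessment should be SD". A worked example has a baseline sum of 200 mm, then 140, 150, 140, 160 and 160 mm. Its result is that "the overall lesion response would be PR - SD - PR - PR - PR", and the text adds: "The second assessment with 140 mm confirms the PR for this subject". Section 7.2.1.2 likewise asks only that the confirming scan come "no less than 4 weeks after the criteria for response are first met".

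Section 10.4.3 opens in agreement: "all confirmed responses (CR or PR) reported up to the analysis cut-off will be included". Its last sentence then says that "subjects with CR or PR at the last radiological assessment prior to cut-off and no response at the previous assessment are by definition unconfirmed", and scores these subjects as non-responders in the primary analysis.

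**The concern.** The last sentence of Section 10.4.3 tests only the scan immediately before the last one. Appendix 2 tests for any earlier response that is at least 4 weeks older and precedes progression. A subject with PR, then SD, then PR at the last scan passes the second test and fails the first. So does a subject whose middle scan is UNK, which Appendix 2 assigns by default after a change of imaging method.

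The primary endpoint therefore takes two values for one record, depending on which section is programmed. Under Section 10.4.3 the value also changes once a later assessable scan arrives, although the two responses that confirm each other are the same. The supportive central-review ORR uses the same conventions (Section 10.4.4), so it would not reveal the problem. Duration of response is summarised in subjects with a confirmed best response (Section 10.5.1), so its population would either lose these subjects or disagree with the ORR numerator.

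**Working it through.** **Step 1: reproduce the Appendix 2 example.** Change from baseline = (sum − 200)/200. Increase from nadir = (sum − nadir)/nadir. PR needs a change of −30% or lower; PD needs an increase from nadir of at least 20% and at least 5 mm (Table 14-5).

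- 140 mm: −60/200 = −30%, PR.
- 150 mm: −50/200 = −25%; from nadir 10/140 = +7.1%; SD.
- 140 mm: −30%, PR. This is the second PR, so the response is confirmed.
- 160 mm, twice: −40/200 = −20%; from nadir 20/140 = +14.3%, so not PD; carried as PR because confirmation has been reached.

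The result is PR-SD-PR-PR-PR with confirmation at scan 3, as the protocol states. On the Section 7.2.1.2 schedule (weeks 12, 20, 28), scans 1 and 3 are 28 − 12 = 16 weeks apart, so the 4-week condition is met.

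**Step 2: apply both rules to short records ending at cut-off.**

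| Scans | Appendix 2 | Section 10.4.3 as worded |
|---|---|---|
| SD-PR | non-responder | non-responder |
| PR-SD | non-responder | non-responder |
| PR-PR | responder | responder |
| PR-SD-PR | **responder** | **non-responder** |
| PR-UNK-PR | **responder** | **non-responder** |
| PR-SD-PR-PR | responder | responder |
| PR-SD-PR-SD | responder | responder |

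With two scans, Appendix 2 gives a responder only if both are responses, and then the Section 10.4.3 sentence does not apply. The conflict therefore needs at least three post-baseline scans.

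**Step 3: who can have three scans.** An arm 1A interim is triggered once subjects have two post-baseline assessments or have stopped treatment (Section 4.2.2). Subjects with only those two scans are unaffected. Those who can be affected are:

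- subjects enrolled earlier, including the part 1 subjects when the second interim is run;
- subjects with a separate confirmatory scan, for example at weeks 12, 16 and 20;
- subjects at the primary analysis, where at least 9 months of follow-up gives scheduled scans at weeks 12, 20, 28 and 36.

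**Step 4: what one responder does at the arm 1A boundaries.** The interim posterior is Beta(y+1, n−y+1), and the arm passes if P(ORR ≥ 20%) > 70% (Table 10-4). The final test requires the lower exact 95% limit to exceed 15% (Section 10.4.2.2).

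| Look | At the boundary | One fewer |
|---|---|---|
| First interim | 5/20: 76.9%, passes | 4/20: 58.6%, futile |
| Second interim | 9/40: 70.4%, passes | 8/40: 56.2%, futile |
| Final | 23/100: 15.2% to 32.5%, rejects H0 | 22/100: 14.3% to 31.4%, does not reject |

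The interim figures match Tables 10-5 and 10-6, and the 23/100 interval matches Table 10-11. The 22/100 interval was computed in the same way.

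**The case against.** The strongest reply is that the sentence only illustrates the rule before it. Section 10.4.3 starts by including every confirmed response, and the disputed sentence is offered as a special case of responses already unconfirmed. Its natural target is a first response at the last scan, such as SD-PR, where both texts agree. That was probably the intent. It does not rescue the wording, which names the immediately preceding scan and makes the result definitional. A programmer working from the primary-endpoint section could code it as written.

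It can also be said that the effect is conservative and narrow. Both are true. The rule only removes responders, so it cannot inflate the type I error. It needs a second response at the last scan directly after an SD or UNK, and the texts agree again once a later assessable scan exists. Interim decisions also weigh duration of response, safety and biomarker data. All four randomized arms had been declared futile by Amendment 5, so the practical reach is arm 1A. These points limit the size of the problem but leave the contradiction in place.

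Leaving the matter to the SAP would not resolve it, since an SAP would have to depart either from Section 10.4.3 or from Appendix 2.

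**Conclusion.** The contradiction stands on the text alone and needs no outside assumption. Followed literally, Section 10.4.3 drops some subjects who are confirmed responders under the definition adopted for the primary ORR.

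Three stronger readings are tempting and are not supported:

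- **That the interims are hit hardest.** The trigger is two scans, where the texts cannot conflict. The interim effect is confined to subjects with three or more scans.
- **That a known percentage of responders is lost.** The protocol gives no scan noise, depth of response, progression rate or rate of unassessable scans. Assuming a true change of mean −5% and SD 35%, noise SD of 5 to 10%, 15% progression per scan and 0 to 5% UNK, simulation gives a loss of about 4 to 7% of confirmed responders if every cut falls at the third scan, and about 2 to 5% at the fourth. Those figures follow from the assumptions and should not be quoted as the size of the effect.
- **That the boundary reversals are the expected effect.** They show what any single responder does at a boundary. They justify removing an avoidable ambiguity in the count; they do not predict a wrong decision.

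**What to change.** Replace the last sentence of Section 10.4.3 with:

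> A CR or PR at the last assessment before cut-off is unconfirmed if there is no other CR or PR at an assessment at least 4 weeks earlier, with both determinations before progression; such subjects, unless already confirmed per Appendix 2, are non-responders for the primary analysis.

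Requiring both determinations before progression keeps PR-PD-PR from counting, which matters because treatment beyond progression is allowed (Section 6.1.5.1). The exception for subjects already confirmed protects someone with two qualifying responses before progression and a further response afterwards. With this wording, PR-SD-PR and PR-UNK-PR count as confirmed and SD-PR stays unconfirmed, as in Appendix 2. The cost is one sentence in the protocol and matching code; no data collection, visit or sample size changes.
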